6.2.4.1. Variables

The following covariates are used for stratification and postcalculation.

- Gender: female or male
- Age: will be calculated as the difference between the data of start of treatment and the birth month and year (for all patients considered the 1st of every month).
- Weight: the weight of an included patient a prior to the start of treatment with immunoglobulins

6.2.4.2. Stratification variables

Stratification by gender with strata:

- men
- women

The patients will be stratified based on age, yielding two strata:

- Age \geq 16
- Age < 16

Extravascular + intravascular stratification with strata:

- Extravascular
- Intravascular

Stratification by hospital with strata:

- HUVH

- HUB
- HGTiP

Stratification on ICD10-codes*

- A00-B99 Certain infectious and parasitic diseases
- C00-D49 Neoplasms
- D50-D89 Diseases of the blood and blood-forming organs and certain disorders involving the immune mechanism
- E00-E89 Endocrine, nutritional and metabolic diseases
- F01-F99 Mental, Behavioral and Neurodevelopmental disorders
- G00-G99 Diseases of the nervous system
- H00-H59 Diseases of the eye and adnexa
- H60-H95 Diseases of the ear and mastoid process
- I00-I99 Diseases of the circulatory system
- J00-J99 Diseases of the respiratory system
- K00-K95 Diseases of the digestive system
- L00-L99 Diseases of the skin and subcutaneous tissue
- M00-M99 Diseases of the musculoskeletal system and connective tissue
- N00-N99 Diseases of the genitourinary system
- O00-O9A Pregnancy, childbirth and the puerperium
- P00-P96 Certain conditions originating in the perinatal period
- Q00-Q99 Congenital malformations, deformations and chromosomal abnormalities
- R00-R99 Symptoms, signs and abnormal clinical and laboratory findings, not elsewhere classified
- S00-T88 Injury, poisoning and certain other consequences of external causes
- U00-U85 Codes for special purposes
- V00-Y99 External causes of morbidity
- Z00-Z99 Factors influencing health status and contact with health services

**ICD-10 dictionary corresponds to its Spanish version named CIE-10.*

6.3. Validation of the RPT (objective 2)

Validation is often reported as a quality marker for both the results of the research and of the records used (Nicholson, 2011). Validation indicates the process of assessing and improving register quality. One of the objectives is to validate the indications for use of the non-specific immunoglobulins of the RPT of the HUVH, HUB and HGTiP. The RPT plays a crucial role in this multi-centered study. Obtaining reliable results requires valid diagnosis. Data are considered valid if the data represent what they claim to represent. This external validation will measure the accuracy of the data in the RPT. For the RPT validation of the diagnosis the information recorded in the electronic health record, SAP of the participating hospitals, will be used as “gold standard”. In validity studies, the gold standard is assumed to represent the true value and thus to be free of error. The validation of the RPT will be stratified by age, indication and hospital.

6.3.1. Sample size calculation

For the sample size calculation for the validation of the indications in the RPT, the Granmo online calculator was used (https://www.imim.es/ofertadeserveis/en_granmo.html). It was determined that for a total of 500 RPT records, a random sample of 173 individuals was sufficient to estimate the validity of the register with a confidence interval of 95% and a precision of +/- 5%. The expected proportion was 78%, based on a similar previous study (R. Izquierdo et al 2020) and a replacement rate was not taken into account due to study validation design.

Of the 500 records, 224 belong to the Vall d'Hebron Hospital. This means that, with the same conditions as mentioned above, the sample size of the validation for the Vall d'Hebron Hospital will be 122. The number of validations is calculated in the same way for the other hospitals.

6.3.2. Validation form

A validation form has been built using RedCap (RedCap, 2019). This standard validation form is user-friendly and should be used across multiple centers to ensure proper validation and uniformity of information. The form includes sex, year of birth, indication of RPT (including ICD10) and indication(s) of SAP (including ICD10). Finally, the reviewer can mark the matching status as correct, missing, incorrect and doubtful. If the **full** code in the RPT corresponds with the code in the clinical history the status could be classified as correct. Missing means that the reviewer has not enough information in either RPT or SAP to draw a conclusion. The reviewer can mark a case as incorrect when the two diagnoses are not equivalent or do not belong to the same ICD subgroup. When there is no code in the clinical history the diagnosis would be written down as free text, these cases will be reviewed case by case. In case of doubt, the reviewer can specify the doubt in the form. Doubtful cases will be discussed and a consensus will be reached within the research team. All cases will be reviewed by two different observers in order to map out the reliability of the validation [see *paragraph 6.3.3.*]. This form can be found in Annex 8.

6.3.3. Specific methods for validation

There are different methods used for the assessment of validity. Which index or technique is used depends on the type of variable. In this case, the variable is categorical. The positive predictive value is used for validation of the RPT. To make sure the validation is reliable the Cohen's kappa score and percent agreement will be calculated. There are other methods that could be used for validation but cannot be applied in the validation of the RPT (Szklo, 2014). These methods can be found in annex 9.

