6.2.1. Exposures

All the patients included in the study are exposed to non-specific immunoglobulines, this could be an extra- (J06BA02) or intravascular (J06BA01) administration.

List of definitions:

Naive incident user: a patient who isn't exposed to immunoglobulines (intra- or extravascular) a year prior to the start of the treatment with a non-specific immunoglobulin.

Immunoglobulin switching: the patients who changed immunoglobulin therapy from extravascular to an intravascular administration or vice versa during the study period providing that the period in between therapies is less than a year, regardless of the indication. In cases where two immunoglobulin types overlap in time, we won't consider them as switchers.

Immunoglobulin concomitance: if an overlapping use of an intravascular and an extravascular immunoglobulin of at least one day, regardless of indication. If cases are found they will be narratively described.

Immunoglobulin discontinuation: the patients who stopped the use of any type of non-specific immunoglobulines (J06BA01 and J06BA02) for a year or longer.

Duration of treatment: When there is a certain period between the start date and end date of the use of immunoglobulin.

Patients with multiple indications: In RPT each treatment initiation is linked to a single indication. When a patient meets multiple treatment initiations, different diagnosis for each may be found. In this case, if the patient does not meet any of the previous definitions (switching or discontinuation) and is treated with the same type of IGG administration (extra- or intravascular), they will be reviewed case by case. From this review, it will be decided based on medical criteria whether diagnoses are a specification of the other (e.g., transplant versus transplant rejection), or if they are clearly referring to different clinical entities. For both situations, if cases are found they will be narratively described.

These group of patients will not be taken into account during the validation of the RPT (see 6.3).

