6.3.3.1. Positive predictive values

The positive predictive value is a measure used in the context of the evaluation of screening and diagnostic procedures, in addition to sensitivity and specificity [annex 9], the positive predictive value (PVV) is the proportion of patients truly diagnosed as positive to all those who had positive test results (Szklo, 2014). In this validation, the PVV is calculated by dividing the cases with diagnosis in RPT which are equivalent to the clinical history to all the cases of RPT indications ($A/(A+B)$), according to figure 1.

		CLINICAL HISTORY (CH)		
		YES	NO	TOTAL

RPT REGISTER	YES	A Diagnose in RPT equal* to CH (VP)	B Diagnose in RPT different than CH or absent	POSITIVES
	NO	C No Diagnose in RPT	D No Diagnose in RPT and no DX in CH	NEGATIVES
	TOTAL	DX in CH		

Figure 1: measures of validity of categorical data. Sensitivity: $A/(A+C)$; specificity $B/(B+D)$; positive predictive value: $A/(A+B)$; negative predictive value $D/(C+D)$.

[figure not shown]
*If the full code in the RPT corresponds with the code in the clinical history the status could be classified as correct. When there is no code in the clinical history the diagnosis would be written down as free text, these cases will be reviewed case by case.

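### PPV is made the only validity measure and others are ruled out, yet the sample and form already allow sensitivity per indication among registered users, which is needed to see under-counting

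*SAP*

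**What the plan says.** Section 6.3.3 of the SAP chooses one validity measure: "The positive predictive value is used for validation of the RPT". Kappa and percent agreement are added as checks of reliability. It then states: "There are other methods that could be used for validation but cannot be applied in the validation of the RPT", and refers to Annex 9. Section 6.3.3.1 places sensitivity and specificity in that annex ("in addition to sensitivity and specificity [annex 9], the positive predictive value (PVV"), so they are among the measures set aside. The body gives no reason, and the annex text is not available to us.

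The design is described elsewhere in the SAP:

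- **Sampling (6.3.1):** "a random sample of 173 individuals was sufficient to estimate the validity of the register", drawn from 500 RPT records.
- **Data per case (6.3.2):** "indication of RPT (including ICD10) and indication(s) of SAP (including ICD10". Here the abbreviation SAP means the hospitals' electronic record system.
- **Reference (6.3):** the hospital record is the gold standard and is taken to be free of error. Results are to be stratified by age, indication and hospital.
- **RPT structure (6.2.1):** "In RPT each treatment initiation is linked to a single indication".

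Figure 1 defines the NO row as records with no diagnosis in the RPT at all. Its caption prints "specificity $B/(B+D" and closes the bracket there.

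**The concern.** Because every RPT initiation carries an indication, the NO row of Figure 1 is almost empty by construction, and sensitivity then seems out of reach. That follows from treating a variable with many categories as diagnosis present or absent. For a given indication, the useful NO row is records filed in the RPT under a different indication, and the form captures those.

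Objective 1 reports the proportion of patients per indication and per evidence group (6.2.2, 6.2.4), and section 8.1 justifies the validation by the registry's role in that objective. Such a proportion can be wrong in two directions: records placed in an indication that do not belong there, and records that belong there but sit elsewhere. PPV by RPT indication measures the first. It does not show which indication suffers the second.

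**Working it through.** **1. The plan's own sample size.** Inputs from 6.3.1: expected proportion 0.78, 95% confidence, half-width 0.05, N = 500 overall and 224 for Vall d'Hebron.

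- n0 = 1.96² × 0.78 × 0.22 / 0.05² = 263.7
- n = n0 / [1 + (n0 − 1)/N]
- N = 500: 172.9, so 173 (stated 173)
- N = 224: 121.4, so 122 (stated 122)

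Both figures are reproduced and are not in dispute.

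**2. Are all four cells available per indication?** Take any indication k and cross-tabulate the two codes:

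| Cell | RPT code | Clinical-history code |
|---|---|---|
| A | k | k |
| B | k | not k |
| C | not k | k |
| D | not k | not k |

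A record with RPT code j and chart code k is a B for j and a C for k. PPV = A/(A+B), sensitivity = A/(A+C) and specificity = D/(B+D) then need no data beyond the form. The sample is not selected on indication, so A/(A+C) estimates sensitivity among registered users, after hospital weighting if the hospitals are pooled.

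**3. Does PPV determine sensitivity?** Use n = 173 and the expected 78%: about 135 records match and 38 do not. Assume an indication with 20 RPT records, 18 of them confirmed (A = 18, B = 2). Between 0 and 36 of the other mismatches could belong to it in the chart. Intervals are unweighted 95% Wilson intervals.

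| C | PPV | Sensitivity |
|---|---|---|
| 0 | 90% (70–97%) | 100% (82–100%) |
| 2 | 90% (70–97%) | 90% (70–97%) |
| 10 | 90% (70–97%) | 64% (46–79%) |
| 20 | 90% (70–97%) | 47% (32–63%) |
| 36 | 90% (70–97%) | 33% (22–47%) |

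**4. Effect on an objective 1 proportion.** Since A is counted from both sides, true count × sensitivity = RPT count × PPV. With an assumed RPT share of 20% and a PPV of 78%, A is 20% × 0.78 = 15.6% of records.

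- Sensitivity 95% (assumed): 15.6% / 0.95 = 16.4%
- Sensitivity 60% (assumed): 15.6% / 0.60 = 26.0%

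How demanding is the 60% case? If the overall match rate is also 78%, mismatches are 22% of records. Of these, 20% × 0.22 = 4.4 points lie in this indication's own RPT records, leaving 17.6. The 60% case needs 26.0 − 15.6 = 10.4 of those, or 59%. The 95% case needs 16.4 − 15.6 = 0.8, or about 5%.

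**5. Specificity.** In Figure 1, B is RPT yes with clinical history no, and D is no on both. B/(B+D) is therefore 1 minus specificity. In step 3 at C = 20, D = 173 − 18 − 2 − 20 = 133. The correct value is 133/135 = 98.5%, and the printed formula gives 2/135 = 1.5%.

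**6. Sampling fractions.** Vall d'Hebron is sampled at 122/224 = 54%, against 173/500 = 35% overall. The other two hospitals are to be calculated in the same way. Fractions therefore generally differ by hospital, and pooled estimates need weights.

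**The case against.** The strongest reply is that the plan's statement is true in its own terms. With the NO row meaning no diagnosis in the RPT, and sampling confined to RPT records, ordinary sensitivity cannot be estimated. Treated patients who were never registered are invisible to this design. That stands. What is proposed here is a different quantity, conditional on registration, and Annex 9 may give a reason that we cannot see. A reason based on the empty NO row would still not exclude the cross-table.

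Other points also stand:

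- **PPV is a fair measure of the accuracy of recorded indications.** With one code on each side, overall sensitivity equals overall PPV, so the gain is only per indication. Stratification by indication is, however, what section 6.3 promises.
- **The chart may list several indications**, and there are free-text, missing and doubtful cases. A rule is needed before cell C can be counted.
- **Precision will be low** for single codes.
- **The planned output is not blind.** Each misfiled record lowers the PPV of the indication it was filed under, so the stratified PPVs limit the total under-recording. They do not say where it falls. Nor does one overall kappa, although 6.3.3.2.2 describes kappa as RPT-to-record agreement.

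Stronger conclusions that a reader might infer are not supported. The documents do not show that the planned PPV is invalid, that any indication is in fact under-recorded, or that registration completeness could be assessed. The misprinted specificity distorts no planned result, because only A/(A+B) is to be calculated and that formula is right.

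**Conclusion.** The concern holds in a limited form. The exclusion of other validity measures is correct for unregistered patients and for Figure 1 as drawn. It is too broad per indication, where sensitivity among registered users can be estimated from data already planned, and where PPV leaves it undetermined (33% to 100% in the example with PPV fixed at 90%).

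The shift from 16.4% to 26.0% is an illustration. It rests on an assumed 20% share, assumed sensitivities of 95% and 60%, and the use of the plan's expected 78% as this indication's PPV. The upper end needs about 59% of all other mismatches to fall on one indication. At chapter or evidence-group level, mismatches within the same group drop out, so the effect may be smaller. All of this takes the hospital record as true, as section 6.3 does, and does not cover the patients with multiple indications whom 6.2.1 leaves out of the validation.

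The cross-table is a worthwhile, inexpensive addition. The specificity formula is a minor text correction.

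**What to change.** 1. **Section 6.3.3:** limit the statement on inapplicable methods to registration completeness, that is, treated patients absent from the RPT. Then add: *From the cross-tabulation of RPT indication by clinical-history indication we report PPV and sensitivity among registered users, each with a 95% confidence interval, for evidence groups and for ICD chapters or the main indications. Pooled estimates are weighted by the inverse of the hospital sampling fraction.*
2. **Counting rules (6.3.2):** where the chart holds several indications, use the one for which the immunoglobulin was started. Do not count a record as a false negative for another indication if its RPT code is confirmed by the chart. Show missing and unresolved cases separately. Apply the same matching level to PPV and sensitivity within each table.
3. **Figure 1:** for the per-indication table, define the NO row as another indication in the RPT, and change specificity to D/(B+D).

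The cost is one more table, a short set of counting rules and small text edits. Both codes are already on the form, but the reviewers must identify the treated indication when the chart lists several. Estimates for rare indications will be imprecise, which is why grouping and intervals are needed.

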6.3.3.1. Positive predictive values

The positive predictive value is a measure used in the context of the evaluation of screening and diagnostic procedures, in addition to sensitivity and specificity [annex 9], the positive predictive value (PVV) is the proportion of patients truly diagnosed as positive to all those who had positive test results (Szklo, 2014). In this validation, the PVV is calculated by dividing the cases with diagnosis in RPT which are equivalent to the clinical history to all the cases of RPT indications ($A/(A+B)$), according to figure 1.

		CLINICAL HISTORY (CH)		
		YES	NO	TOTAL

RPT REGISTER	YES	A Diagnose in RPT equal* to CH (VP)	B Diagnose in RPT different than CH or absent	POSITIVES
	NO	C No Diagnose in RPT	D No Diagnose in RPT and no DX in CH	NEGATIVES
	TOTAL	DX in CH		

Figure 1: measures of validity of categorical data. Sensitivity: $A/(A+C)$; specificity $B/(B+D)$; positive predictive value: $A/(A+B)$; negative predictive value $D/(C+D)$.

[figure not shown]
*If the full code in the RPT corresponds with the code in the clinical history the status could be classified as correct. When there is no code in the clinical history the diagnosis would be written down as free text, these cases will be reviewed case by case.

6.3.3.2. Reliability of the validation

In addition to validity, reliability is also taken into account. The reliability says something about the extent to which the results can be reproduced when the research is repeated under the same conditions. It is assessed by checking the consistency of results across time, across different observers, and across parts of the test itself (Szklo, 2014).

6.3.3.2.1. Percent agreement

Percent agreement is a simple method of summarizing agreement for categorical variables and thus could be used to examine the reliability of the validation of the RPT. Percent agreement between two sets of observations is obtained by dividing the number of paired observations in the agreement cells by the total number of paired observations. The percent agreement calculation is shown in figure 2. The observation numbers could be obtained by two different reviewers or by the same reviewer at two different points in time (Szklo, 2014). To check the reliability of the RPT validation two different reviewers will fill in the validation form (annex 8) for the same case. The cases of the two different reviewers will be compared and divided into groups according to figure 3.

$$\text{Percent agreement: } \frac{(a + d)}{(a + b + c + d)} \times 100$$

Figure 2: Percent agreement for paired binary test

	Observer 2		
		Correct	Incorrect
Observer 1	Correct	A Correct by both	B Correct by observer 1, incorrect by observer 2
	Incorrect	C Correct by observer 2, incorrect by observer 1	D Incorrect by both

Figure 3: Percent agreement to check reliability of the validation of RPT

6.3.3.2.2. Cohen Kappa

The kappa statistic is defined as the fraction of the observed agreement not due to chance in relation to the maximum non-chance agreement when using a categorical classification of a variable (Szklo, 2014). This method is used in this specific validation to measure the percentage agreement between the RPT and SAP beyond that expected by chance alone.

The formula for Cohen's kappa is defined as:

$$k = (p_o - p_e) / (1 - p_e)$$

where **P_o** is the relative observed agreement among raters (= percent agreement calculated above) and **P_e** is the hypothetical probability of chance agreement.

The chance agreement is the agreement that would be expected if both observers rated the responses at random. The total chance agreement is the sum of the chance agreement for each cell on the diagonal. The number expected in each cell by chance alone is the product of the corresponding marginal totals divided by the grand total. Using the notation in figure 2 the following calculation is given:

$$Pe = (a + c) \times (a + b) + (b+d) \times (c+d) / (a+b+c+d)^2$$

Kappa = 0: the amount of agreement that can be expected from random chance

Kappa = 1: perfect agreement between the raters

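### Kappa is described as registry-versus-record agreement but is built on the two-reviewer table; its chance-agreement formula lacks brackets, and missing and doubtful ratings have no cell

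*SAP*

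**What the plan says.** In the plan, SAP is also the name of the hospitals' electronic record (section 6.3). Below, that system is called the hospital record and the document is called the plan.

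- **Purpose of kappa, section 6.3.3.2.2.** "This method is used in this specific validation to measure the percentage agreement between the RPT and SAP beyond that expected by chance alone".
- **Purpose of kappa, section 6.3.3.** "To make sure the validation is reliable the Cohen's kappa score and percent agreement will be calculated". The same section assigns validation of the RPT to the positive predictive value (PPV), defined in section 6.3.3.1.
- **Observed agreement, section 6.3.3.2.2.** Po "is the relative observed agreement among raters (= percent agreement calculated above". The calculation above it is the percent agreement of section 6.3.3.2.1, where "The cases of the two different reviewers will be compared and divided into groups according to figure 3". Figure 3 crosses observer 1 with observer 2, each rating Correct or Incorrect.
- **Chance agreement, section 6.3.3.2.2.** The formula is printed as "Pe = (a + c) \times (a + b) + (b+d) \times (c+d) / (a+b+c+d)^2". The prose just before it takes, for each diagonal cell, the product of the two margins over the grand total, and adds the diagonal cells.
- **Rating categories, section 6.3.2.** On the form "the reviewer can mark the matching status as correct, missing, incorrect and doubtful". For one of these, "Doubtful cases will be discussed and a consensus will be reached within the research team". The plan does not say whether the agreement table is filled before or after that discussion, or where a rating of missing goes.

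**The concern.** Objective 2 is to validate the indications recorded in the RPT. Two different quantities matter: how often the RPT indication matches the hospital record (validity), and how consistently two people judge that match (reliability). The kappa section names the first and calculates the second. Two reviewers can agree closely while many RPT codes are wrong, so someone working from that sentence alone could present a reliability figure as registry accuracy.

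The formula and the table raise a separate problem: neither can be carried out exactly as printed. An analyst who codes the formula literally with counts gets a meaningless kappa. An analyst filling figure 3 must decide what to do with two of the four permitted ratings, possibly after seeing the data.

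**Working it through.** **1. What kappa measures.** Each element of section 6.3.3.2.2 points to the two reviewers: Po is the percent agreement of figure 3, chance agreement is described for two observers rating at random, and a value of 1 is described as agreement between raters. Figure 3 contains only verdicts on whether a code matched. Chance-corrected agreement between RPT and hospital record would need a table of RPT indications against record indications, and the plan sets up none for kappa.

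**2. The formula.** The plan gives no numerical Pe or kappa to reproduce. The examples use N = 173, the sample size of section 6.3.1. That figure reproduces: 1.96² × 0.78 × 0.22 / 0.05² = 263.7, and the finite-population correction for 500 records gives 172.6 to 172.9, rounded up to 173. The cell counts are assumptions.

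- As printed: Pe = (a+c)(a+b) + [(b+d)(c+d)/N²]
- Bracketed: Pe = [(a+c)(a+b) + (b+d)(c+d)]/N²
- Both: kappa = (Po − Pe)/(1 − Pe), with N² = 29,929

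For (105, 30, 30, 8), where each reviewer rates 135 of 173 (78%) correct, Po = 113/173 = 0.6532.

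- Printed Pe = 135 × 135 + 38 × 38/29,929 = 18,225.05. Kappa = (0.6532 − 18,225.05)/(1 − 18,225.05) = 1.00002.
- Bracketed Pe = (18,225 + 1,444)/29,929 = 0.6572. Kappa = (0.6532 − 0.6572)/0.3428 = −0.012.

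| a, b, c, d | Printed Pe | Printed kappa | Correct Pe | Correct kappa |
|---|---|---|---|---|
| 120, 8, 10, 35 | 16,640.06 | 1.000006 | 0.621 | 0.726 |
| 105, 30, 30, 8 | 18,225.05 | 1.00002 | 0.657 | −0.012 |
| 5, 80, 80, 8 | 7,225.26 | 1.0001 | 0.500 | −0.850 |
| 2, 1, 1, 169 | 9.97 | 1.001 | 0.966 | 0.661 |

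The reason is algebraic: printed kappa exceeds 1 by (1 − Po)/(Pe − 1), which is tiny once (a+c)(a+b) is large. If a to d are proportions summing to 1, the divisor is 1 and the printed line is correct: for the second row, 0.7803² + 0.2197² = 0.657.

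**3. Ratings without a cell.** Assume 173 charts, of which 147 fall in the 2×2 table as (115, 5, 5, 22) and 26 are rated missing or doubtful by at least one reviewer.

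- **2×2 only:** Po = 137/147 = 93.2%; Pe = (120² + 27²)/147² = 0.700; kappa = 0.77.
- **Both reviewers rate all 26 missing:** Po = 163/173 = 94.2%; Pe = (120² + 27² + 26²)/173² = 0.528; kappa = 0.88. Excluding the 26 lowers both measures.
- **Reviewers agree on 18 of the 26** (missing and doubtful pooled as a third category; the other 8 spread evenly, 2 per off-diagonal cell): Po = 155/173 = 89.6%; Pe = (122² + 29² + 22²)/173² = 0.542; kappa = 0.77. For kappa this is the break-even.
- **Reviewers agree on 6 of the 26** (the other 20 spread evenly, 5 per cell): Po = 143/173 = 82.7%; Pe = (125² + 32² + 16²)/173² = 0.565; kappa = 0.60. Excluding the 26 raises both measures.

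The direction therefore depends on how well reviewers agree on these charts, which the plan cannot tell us. Entering doubtful cases after consensus raises a different issue: both entries then carry one joint decision and are no longer two independent ratings.

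**The case against.** The strongest reply is that these are wording faults in a supporting statistic. Sections 6.3.2, 6.3.3 and 6.3.3.2.1, and most of 6.3.3.2.2, treat kappa as reliability between reviewers, and validity is assigned to the PPV. The prose definition of chance agreement is correct, standard software would compute kappa properly, and a Pe in the thousands or a kappa above 1 would expose the slip. Kappa does not enter the PPV, the sample size, the costs or any objective 1 result. All of this stands, and it limits the weight of the point.

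Three stronger readings are tempting, and the document does not support them.

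- **The printed formula gives chance agreement of about 1, or perfect agreement for any data.** It is kappa that lands near 1. Pe is far above 1, and only when counts are entered and (a+c)(a+b) is large.
- **Figure 3 inflates agreement by dropping the hard cases.** The plan does not say these cases are dropped, and the calculation above shows that exclusion can lower agreement as well as raise it. A rating of missing means there is too little information to judge, and two reviewers may well agree on that. Collapsing to correct versus not correct is another possible route; figure 1 already puts a different and an absent diagnosis in one cell.
- **A high kappa will be reported as proof that the RPT is valid.** One sentence invites this, but the PPV would be reported as well. In the extreme case where both reviewers call every code wrong, percent agreement is 100%, the PPV is 0 and kappa is undefined.

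The reply leaves three things unanswered: the stated purpose contradicts the calculation, the printed formula is wrong for counts, and no rule covers missing ratings or the timing of consensus.

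**Conclusion.** The point holds as a correction that should be made before the ratings are analysed; it does not threaten the main results. The stated target of kappa is wrong: as constructed, it measures inter-reviewer reliability and cannot measure agreement between RPT and hospital record. The printed Pe is wrong for cell counts and makes kappa about 1 for nearly any table, for example 1.00002 instead of −0.01. It is most likely typographical, given the correct prose and its validity for proportions. The handling of missing and doubtful ratings is open. Under the assumed tables, using all 173 charts gives a kappa of 0.60 to 0.88, against 0.77 for the 2×2 alone, so neither the size nor the direction of the effect can be fixed in advance. The first conclusion rests on the text alone; the numerical ones rest on assumed counts, because the plan gives none.

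**What to change.** - **Purpose.** State in section 6.3.3.2.2 that percent agreement and kappa measure agreement between the two reviewers, and that they are not measures of RPT validity, which the PPV gives.
- **Formula.** Print Pe = [(a+c)(a+b) + (b+d)(c+d)] / (a+b+c+d)². For four categories, use the sum over categories of the product of the two reviewers' margins, divided by N².
- **Table.** Compute both measures on the independent ratings made before consensus, for all reviewed cases, using correct, missing, incorrect and doubtful. A prespecified collapse to correct versus not correct is an acceptable alternative. Report the correct/incorrect 2×2 as well, with the number of cases outside it.

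The cost is a short amendment to the text and a few lines of code, provided each reviewer's pre-consensus rating is kept. The downside is that reported reliability may change and could be lower. The choice of categories should be fixed before the ratings are tabulated, since it would be hard to defend afterwards.
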